4.3. Prohibitions and Restrictions

Potential subjects must be willing and able to adhere to the following prohibitions and restrictions during the course of the study to be eligible for participation:

- 1. Agree to follow the contraceptive requirements as noted in Section 4.1 during the main study.
- 2. Criterion modified per Amendment 3:
 - Following vaccination, subjects may be excluded from donating blood products due to induced vaccine seropositivity (see Section 9.4.3) for as long as VISP persists.
- 3. Male subjects must agree not to donate sperm from the first administration of study vaccine or placebo until 3 months after the last dose of study vaccine or placebo.
- 4. Female subjects must agree not to donate eggs (ova, oocytes) for the purpose of assisted reproduction until 3 months after the last dose of study vaccine or placebo.
- 5. See Section 8 for details regarding prohibited and restricted medication during the study.
- 6. Current drug/alcohol use that investigator assesses poses any more than a remotely increased risk of the ability of the subject to comply with the protocol requirements.
- 7. Concurrent participation in another interventional study is disallowed during the main study. Concurrent participation in an observational study without sponsor approval is disallowed during the main study. Subjects who enter the LTE phase are allowed to participate in another clinical study, except for studies with investigational HIV vaccines or other investigational HIV prevention which could be determined to interfere with HIV vaccine response in this study (ie, CD4-Ig depleting Env-specific Abs), which are disallowed and studies with experimental immunomodulators/suppressors which need prior sponsor approval.
- 8. Subjects should be amenable to HIV-risk reduction counseling and committed to maintaining behavior consistent with low risk of HIV exposure through the last required protocol clinic visit.

4.4. Inclusion and Exclusion Criteria for the Long-term Extension Phase

Each potential subject must satisfy all of the following inclusion criteria to be enrolled in the LTE phase of the study upon completion of the final main study visit at Week 72.

- 1. Each subject must sign an ICF appendix for the LTE phase indicating that he or she understands the purpose of and procedures required for the LTE phase and is voluntarily willing to participate in the LTE phase of the study.
- 2. Subject must be randomized to Group 1 or Group 2 of the main study.
 - Note: Upon sponsor unblinding at the Week 28 analysis, subjects randomized to Group 1 or Group 2 who have received all 4 vaccinations, will be asked to participate in the LTE phase and sign the ICF appendix for the LTE phase at Week 72. Subjects who attend their Week 72 visit prior to the sponsor's unblinding at the Week 28 analysis, will be enrolled in the LTE phase if they consent and sign the ICF appendix for the LTE phase and meet the eligibility criteria for the LTE phase. When the Week 28 sponsor unblinding subsequently occurs, subjects that started the LTE phase but turn out to have received placebo in the main study will be withdrawn from the LTE phase.
- 3. Subject must have received all 4 vaccinations of the main study.
- 4. Subject must be negative for HIV infection at the final main study visit at Week 72.
- 5. Subject must be willing/able to adhere to the prohibitions and restrictions for the LTE phase, as specified in the protocol and study procedures.

Any potential subject who meets any of the following exclusion criteria at the end of the main study will be excluded from participating in the LTE phase of the study.

- 1. Subject has any condition for which, in the opinion of the investigator, participation would not be in the best interest of the subject (eg, compromise the well-being) or that could prevent, limit, or confound the protocol-specified assessments.
- 2. Subject is planning to participate in an interventional study during the LTE phase, concerning studies with investigational HIV vaccines or other investigational HIV prevention which could be determined to interfere with HIV vaccine response in this study (ie, CD4-Ig depleting Env-specific Abs), which are disallowed.
- 3. Subject is planning to participate in an interventional study during the LTE phase, concerning an experimental immunomodulator/suppressor that is not allowed per the sponsor. Documentation of the identity of the experimental immunomodulator/suppressor must be provided to the sponsor, who will determine eligibility on a case-by-case basis.

4.5. Inclusion Criteria, Exclusion Criteria and Prohibitions and Restrictions for the Late Boost Vaccination

Assessment of participants' eligibility will be performed within 4-6 weeks before the administration of the late boost vaccination. Each potential participant must satisfy all of the following inclusion criteria to be eligible to receive the late boost vaccination.

- 1. Each subject must sign an ICF appendix indicating that he or she understands the purpose of and procedures required for the late boost vaccination and is voluntarily willing to receive this vaccination.
- 2. Subject must be enrolled in the LTE phase.
- 3. All female subjects of childbearing potential must have a negative serum (β -hCG) at the screening visit, and a negative urine pregnancy test pre-late boost vaccination.
- 4. Contraceptive requirements for heterosexually active female subjects (from 28 days prior to the late boost vaccination up until 3 months after the late boost vaccination)^k:
 - a) If not of childbearing potential: postmenopausal (>45 years of age with amenorrhea for at least 2 years, or any age with amenorrhea for at least 6 months and a serum follicle stimulating hormone [FSH] level >40 IU/L) or surgically sterile: no additional contraception required.
 - b) If of child-bearing potential, but has a vasectomized partner (after vasectomy: sperm count below the limit of detection if procedure occurred <1 year ago¹): no additional contraception required.
 - c) If of child-bearing potential, but has a non-vasectomized partner, or partner had a positive sperm count after a vasectomy procedure of <1 year ago¹, should be practicing an acceptable effective method of contraception. Acceptable methods for this study include:
 - Hormonal contraception,
 - IUD,
 - IUS.
 - Male or female condom with or without spermicide,
 - Cap, diaphragm or sponge with vaginal spermicide, or
 - Sexual abstinence *

*Sexual abstinence is considered an effective method **only** if defined as refraining from heterosexual intercourse during the entire period of risk associated with the study vaccine. The reliability of sexual abstinence needs to be evaluated in relation to the duration of the study and the preferred and usual lifestyle of the subject.

k Verbal assurance should be given that adequate birth control measures have been followed for 28 days prior to the boost vaccination

¹ Based on verbal confirmation

Women who are not heterosexually active at screening, but become sexually active during the time window indicated above must agree to utilize an effective method of birth control as mentioned above.

- 5. Subject must be negative for HIV infection.
- 6. Subject must be willing/able to adhere to the prohibitions and restrictions for late boost vaccination, as specified in the protocol and study procedures.

Any potential participant who meets any of the following exclusion criteria will be excluded from receiving the late boost vaccination.

- 1. Subject has chronic hepatitis B (measured by hepatitis B surface antigen test) or active hepatitis C (measured by hepatitis C virus [HCV] Ab test; if positive, HCV ribonucleic acid (RNA) PCR test will be used to confirm active versus past HCV infection.
- 2. Subject has any condition for which, in the opinion of the investigator, participation would not be in the best interest of the subject (eg, compromise the well-being) or that could prevent, limit, or confound the protocol-specified assessments.
- Subject is planning to participate in an interventional study from signing of the ICF addendum until the end of the study, concerning studies with investigational HIV vaccines or other investigational HIV prevention which could be determined to interfere with HIV vaccine response in this study (ie, CD4-Ig depleting Env-specific Abs), which are disallowed.
- 4. Subject is planning to participate in an interventional study from signing of the ICF appendix until the end of the study, concerning an experimental immunomodulator/suppressor that is not allowed per the sponsor. Documentation of the identity of the experimental immunomodulator/suppressor must be provided to the sponsor, who will determine eligibility on a case-by-case basis.
- 5. Subject is a woman who is pregnant, or breast-feeding, or planning to become pregnant within 3 months after the late boost vaccination.
- 6. Potential participant has had a psychiatric condition or alcohol or drug abuse problems (including hospitalization or periods of work disability) that in the opinion of the investigator would interfere with protocol compliance and thus would preclude participation.
- 7. Potential participant has a history of TTS or heparin-induced thrombocytopenia and thrombosis (HITT)
- 8 Potential participant received or plans to receive:
 - a. Recombinant viral vectored COVID-19 vaccines or live attenuated COVID-19 vaccines, either licensed or authorized for emergency use (eg, Emergency Use Authorization [EUA], Emergency Use Listing [EUL] or similar program) within 28 days before or after planned administration of the late boost study vaccination.

- b. Other COVID-19 vaccines than the ones specified in bullet c (eg, mRNA vaccines, protein-based vaccines) either licensed or authorized for emergency use (eg, EUA, EUL or similar program) within 14 days before or after planned administration of the late boost study vaccination.
- 9 Participant is planning to participate in an interventional study with COVID-19 vaccines, from signing of the ICF appendix until the end of the study.

Potential participants must be willing and able to adhere to the following prohibitions and restrictions to be eligible to receive the late boost extension:

- 1. Agree to follow the contraceptive requirements as noted in the inclusion criterion 4.
- 2. Following vaccination, subjects may be excluded from donating blood products due to induced vaccine seropositivity (see Section 9.4.3) for as long as VISP persists
- 3. Male subjects must agree not to donate sperm from the administration of the late boost until 3 months after the boost vaccination.
- 4. Female subjects must agree not to donate eggs (ova, oocytes) for the purpose of assisted reproduction from the administration of the late boost until 3 months after the boost vaccination.
- 5. See Section 8 for details regarding prohibited and restricted medication during the study.
- 6. Subjects should be amenable to HIV-risk reduction counseling and committed to maintaining behavior consistent with low risk of HIV exposure through the last required protocol clinic visit.

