Aluminum is one of the most common metals found in nature and is present in air, food, and water. Aluminum salts, such as aluminum hydroxide, aluminum phosphate have been used safely in vaccines for more than 70 years. A few studies have reported an association between vaccines containing aluminum adjuvants and persistent nodules at the injection site, at an estimated rate of 0.03% to 0.83%. ^{29,30,31,32} Two studies examining infant exposure to aluminum from both diet and vaccines concluded that aluminum adjuvants at the levels included in vaccines are well below the calculated safe body burden. ^{33,34} A 2017 review found that current data do not support a causal relationship between aluminum-containing vaccines and a variety of autoimmune disorders. ³⁵

Pregnancy and Birth Control

The effect of the study vaccines on a fetus or nursing baby is unknown, as well as the effect on semen, so women of childbearing potential, and men having sexual intercourse with women, are required to agree to practice adequate birth control measures for sexual intercourse from at least 28 days before the first vaccination (or immediately prior to first vaccination for men) until at least 3 months after the last vaccination (see Section 4.1) of the main study and from at least 28 days

before the late boost vaccination until 3 months after the late boost vaccination (see Section 4.5). Women who are pregnant or breast-feeding, or are planning to become pregnant while enrolled in the main study until 3 months after the last vaccination, will be excluded from enrollment into the main study. In addition, women who are pregnant, breast-feeding or planning to become pregnant from screening for the late boost vaccination until 3 months after the vaccination will not be eligible to receive the late boost vaccination.

Risks from Blood Draws

Blood drawing may cause pain/tenderness, bruising, bleeding, becoming lightheaded, dizziness, vaso-vagal response, and, rarely, infection at the site where the blood is taken.

Risks from Human Leukocyte Antigen (HLA) Testing

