- c) If of child-bearing potential, but has a non-vasectomized partner, or partner had a positive sperm count after a vasectomy procedure of <1 year agoⁱ, should be practicing an acceptable effective method of contraception. Acceptable methods for this study include:
 - Hormonal contraception,
 - Intrauterine device (IUD),
 - Intrauterine hormone-releasing system (IUS),
 - Male or female condom with or without spermicide,
 - Cap, diaphragm or sponge with vaginal spermicide, or
 - Sexual abstinence *

*Sexual abstinence is considered an effective method **only** if defined as refraining from heterosexual intercourse during the entire period of risk associated with the study vaccine. The reliability of sexual abstinence needs to be evaluated in relation to the duration of the study and the preferred and usual lifestyle of the subject.

Women who are not heterosexually active at screening, but become sexually active during the study must agree to utilize an effective method of birth control as mentioned above.

- 8. Contraceptive requirements for heterosexually active male subjects (from day of first vaccination until 3 months after last vaccination):
 - a) If male subject had a vasectomy (after vasectomy: sperm count below the limit of detection if procedure occurred <1 year agoⁱ): no additional contraception required.
 - b) If male subject did not have a vasectomy or had a positive sperm count after a vasectomy procedure of <1 year agoⁱ: contraceptive methods will depend on child-bearing potential of female partner: same criteria to be followed as for female subjects in inclusion criterion 7.
- 9. A woman must agree not to donate eggs (ova, oocytes) for the purpose of assisted reproduction after the first dose until 3 months after receiving the last dose of study vaccine or placebo. A man must agree not to donate sperm after the first dose until 3 months after receiving the last dose of study vaccine or placebo.
- 10. Subjects are willing/able to adhere to the prohibitions and restrictions specified in the protocol and study procedures.
- 11. Subjects are amenable to HIV-risk reduction counseling and committed to maintaining behavior consistent with low risk of HIV exposure through the last required protocol clinic visit.

__

ⁱ Based on verbal confirmation

- 12. Subjects are assessed by the clinic staff as being at low risk for HIV infection (for guidelines see Attachment 2).

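### Section 1.2.4 says men must agree to birth control around the late boost and cites Section 4.5, but Section 4.5 asks it only of women

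*Protocol*

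**What the plan says.** In Protocol Section 1.2.4, the paragraph on pregnancy and birth control starts from the unknown effect of the vaccines on a fetus, a nursing baby and semen. One sentence then covers both sexes and both vaccination periods. After women of childbearing potential it continues "and men having sexual intercourse with women, are required to agree to practice adequate birth control measures". For the main study it cites Section 4.1 and gives men their own start, just before the first vaccination. For the boost the period runs from at least 28 days "before the late boost vaccination until 3 months after the late boost vaccination (see Section 4.5"), with no separate start for men.

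Section 4.5 sets the late boost eligibility rules. Inclusion 4 reads "Contraceptive requirements for heterosexually active female subjects (from 28 days prior to the late boost vaccination" and runs until 3 months after it. Restriction 1 reads "Agree to follow the contraceptive requirements as noted in the inclusion criterion 4". Restriction 3 reads "Male subjects must agree not to donate sperm from the administration of the late boost until 3 months after the boost vaccination".

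The main study handles men differently. Section 4.1 criterion 8 is headed "Contraceptive requirements for heterosexually active male subjects (from day of first vaccination until 3 months after last vaccination"). Its part b covers men without an effective vasectomy. It makes the method depend on the partner's childbearing potential, with the "same criteria to be followed as for female subjects in inclusion criterion 7". Section 4.3 restriction 1 limits the reach of these rules: "Agree to follow the contraceptive requirements as noted in Section 4.1 during the main study".

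**The concern.** The risk section presents male contraception around the boost as a requirement and names the section that is supposed to impose it. That section does not. Section 9.1.10 makes compliance with the Section 4.5 inclusion and exclusion criteria the condition for receiving the boost, so a site working from Section 4.5 has no ground to ask a man for this agreement. It would have no deviation to record if he were boosted without it.

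The people exposed are female partners and any pregnancy, neither of whom is a trial participant. This is a safety measure that the protocol claims but does not make a condition. It has no bearing on an endpoint, an estimate or an analysis set.

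**Working it through.** The protocol gives no figure to reproduce, so the check is a reading of every item in Section 4.5 against the statement in Section 1.2.4.

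**Items in Section 4.5.** There are 6 inclusion criteria, 9 exclusion criteria and 6 restrictions, 21 in all. Those touching reproduction are:

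| Item | Applies to | Content |
|---|---|---|
| Inclusion 3 | Women of childbearing potential | Negative pregnancy tests |
| Inclusion 4 | Heterosexually active women | Contraception |
| Exclusion 5 | Women | Pregnant, breast-feeding or planning pregnancy |
| Restriction 1 | All, by wording | Follow inclusion 4 |
| Restriction 3 | Men | No sperm donation |
| Restriction 4 | Women | No egg donation |

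Items requiring contraception of men: 0. Reproductive restrictions specific to men: 1, on sperm donation.

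**Could another rule reach men?**

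- *Restriction 1.* It is addressed to all potential participants but imports only inclusion 4. Parts a to c of inclusion 4 describe a female subject and her partner. No clause carries them over to men, as criterion 8b does in Section 4.1.
- *Section 4.1 criterion 8.* Its end point, 3 months after the last vaccination, might seem to stretch to a fifth dose. But it is a main-study criterion, Section 4.3 confines the Section 4.1 contraceptive requirements to the main study, and Section 1.2.4 cites Section 4.5 for the boost.
- *Section 9.1.10.* Men receive contraceptive counselling at screening and at vaccination. Counselling is neither an agreement nor an eligibility condition.
- *Section 12.3.4.* Partner pregnancies are reported to the sponsor within 24 hours of site awareness. That acts only after conception.

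**Length of the required period for a man having intercourse with women.** Assume 1 month = 30 days. The late boost schedule (footnote 17) states this for visit windows, and it is borrowed here. Then 3 months = 3 × 30 = 90 days.

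| Source | Calculation | Days |
|---|---|---|
| Section 1.2.4, read literally | 28 + 90 | 118 |
| A rule like Section 4.1 criterion 8, from the day of the boost | 0 + 90 | 90 |
| Section 4.5 as written | no rule | 0 |

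For comparison, Section 4.5 asks 28 + 90 = 118 days of a heterosexually active woman of childbearing potential whose partner has not had an effective vasectomy.

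The gap between the first two rows comes from the missing male start time in Section 1.2.4.

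**The case against.** The strongest textual reply is Section 4.5 inclusion 6, which requires willingness to adhere to the late boost prohibitions and restrictions specified in the protocol and study procedures. Section 1.2.4 is part of the protocol, so its statement about men might be read in. This does not work. The late boost prohibitions and restrictions are the list at the end of Section 4.5, which says nothing on male contraception, and Section 1.2.4 itself refers the reader back to Section 4.5.

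Other points carry some weight:

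- **Existing mitigation.** Men are counselled, sperm donation is barred for 3 months, and partner pregnancies are reported. Section 14.1 describes the vectors as replication-incompetent, and Section 1.2.4 calls the risk of vector shedding negligible. No specific partner hazard is identified. This limits the seriousness of the gap, but none of it supplies the agreement that Section 1.2.4 calls required.
- **Consent appendix.** Section 4.5 inclusion 1 requires a signed late boost appendix, where a man's agreement might be recorded. The appendix is not among the documents, so this cannot be checked. Even if it is there, it does not replace a missing eligibility criterion.
- **The 118 days.** This is one reading of an unclear sentence. It is given as a literal reading only.
- **Which section is wrong.** The sponsor may have dropped the male rule on purpose and left Section 1.2.4 too broad. The documents do not exclude this. However, the stated reason, an unknown effect on semen, applies to the boost as much as to the first four doses, and keeping the sperm-donation bar points the same way. In either case the text needs correcting.

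**Conclusion.** The concern holds. Section 1.2.4 states a requirement on men around the late boost and refers it to Section 4.5, where no item imposes it. The required period for a man having intercourse with women is 0 days under Section 4.5, against 118 days under Section 1.2.4 read literally or 90 days under a rule like the main study's. These day counts rest on a 30-day month.

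The mismatch in the text is certain. Its practical reach is not: the documents do not allow a count of the men affected, do not show what the consent appendix asks of them, and do not say whether late boost vaccination is complete. No endpoint or statistical analysis changes. It should be corrected because it concerns the safety of partners and the correction is small.

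**What to change.** Add to Section 4.5 an inclusion criterion for heterosexually active men that mirrors Section 4.1 criterion 8. It should run from the day of the late boost until 3 months after, and its part b should refer to Section 4.5 inclusion 4. Extend restriction 1 to cover the new criterion. State the same male start time in Section 1.2.4 and in the late boost consent appendix.

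An exclusion for men planning to father a child, as in Section 4.2 exclusion 9, would restore consistency with the main study. It is optional, since Section 1.2.4 does not state one. If the sponsor did mean to drop the male requirement for the boost, Section 1.2.4 should say so and give the reason; that fits the semen rationale less well.

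The cost is a few lines in an amendment and in the consent appendix, with no added visits or tests. A few men may decline or be deferred.
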